4.1.2 Exclusion Criteria

A volunteer will be excluded if one or more of the following conditions apply:

Female-Specific Criteria

1. Breast-feeding or planning to become pregnant while participating in the study

Volunteer has received any of the following:

2. More than 10 days of systemic immunosuppressive medications or cytotoxic medications within the 4 weeks prior to randomization or any within the 14 days prior to randomization
3. Blood products within 16 weeks prior to randomization
4. Immunoglobulin within 8 weeks prior to randomization
5. Prior vaccinations with an investigational alphavirus vaccine
6. Investigational research agents within 4 weeks prior to randomization or planning to receive investigational products while on study
7. Live attenuated vaccines within 4 weeks prior to randomization
8. Inactivated vaccines within 2 weeks prior initial study vaccine administration unless approved by the PI
9. Current anti-TB prophylaxis or therapy

Subject has a history of any of the following clinically significant conditions:

10. A history of confirmed or suspected viral encephalitis infection
11. Serious reactions to vaccines that preclude receipt of study vaccinations as determined by the investigator
12. Hereditary angioedema, acquired angioedema, or idiopathic forms of angioedema
13. Asthma that is not well controlled
14. Diabetes mellitus (type I or type II) with the exception of gestational diabetes
15. Thyroid disease that is not well controlled
16. Hypertension that is not well controlled
17. Evidence of autoimmune disease or immunodeficiency
18. Idiopathic urticaria within the last year
19. Malignancy that is active or history of malignancy that is likely to recur during the study

20. Bleeding disorder diagnosed by a doctor (e.g., factor deficiency, coagulopathy, or platelet disorder requiring special precautions) or significant bruising or bleeding difficulties with IM product administration or blood draws
21. Seizure disorder other than: 1) febrile seizures, 2) seizures secondary to alcohol withdrawal more than 3 years ago, or 3) seizures or treatment for a seizure disorder within the last 3 years
22. Asplenia, functional asplenia or any condition resulting in absence or removal of the spleen
23. Psychiatric condition that precludes compliance with the protocol; past or present psychoses; or within 5 years prior to randomization, a history of suicide plan or attempt
24. Any other chronic or clinically significant medical, psychiatric or social condition that, in the judgement of the investigator is a contraindication to protocol participation or impairs a subject's ability to give informed consent.

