4.1.1 Inclusion Criteria

A subject must meet all of the following criteria:

1. Age 18 to 50 years
2. Available for clinical follow-up through 36 weeks after randomization
3. Able to provide proof of identity to the satisfaction of the study clinician completing the enrollment process
4. Able and willing to complete the informed consent process
5. Willing to donate blood for sample storage to be used for future research
6. In good general health, without clinically significant medical history, and has satisfactorily completed screening
7. Physical examination and laboratory results without clinically significant findings within the 28 days prior to randomization

Laboratory Criteria within 28 days prior to randomization:

8. Hemoglobin within institutional normal range or accompanied by Principal Investigator (PI) or designee approval
9. White blood cell (WBC) differential either within institutional normal range or accompanied by PI or designee approval
10. Total lymphocyte count: ≥ 800 cells/mm³
11. Platelets: 125,000-500,000/mm³
12. Alanine aminotransferase (ALT): ≤ 1.25 x upper limit of normal range
13. Serum creatinine: ≤ 1.1 x upper limit of normal
14. Negative for HIV infection by an FDA-approved method of detection

Criteria applicable to women of childbearing potential

15. Negative beta-human chorionic gonadotropin (β -HCG) pregnancy test (urine or serum) on day of randomization before receiving the study product
16. Agrees to use an effective method of birth control, if sexually active, from at least 21 days prior to randomization through the last study visit.

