- **HIV Prevention Counseling:** During screening, HIV counseling must be completed on all subjects being tested for HIV to ensure the subject is aware of how to reduce risk of and avoid HIV infection. Every attempt must be made to provide the HIV test results to the subjects.
- **Blood Sample Collection:**
 - Samples for clinical evaluation of eligibility criteria must be collected no more than 28 days before randomization. Tests may be repeated as needed based on clinical judgment to confirm eligibility or if there is a suspected change in health status.
 - Samples for research must be collected during screening per Schedule of Evaluations (Appendix III). However, research samples obtained more than 28 days before randomization do not need to be repeated. Some samples collected during screening may be used for assay validation and site proficiency testing.
- **Eligibility Review:** Based on results from the physical examination, medical history evaluation, blood tests and any additional health assessments performed during screening, the study clinicians will determine if subjects qualify to be randomized and receive the study product, and confirm this by documenting on the applicable data collection forms and in the database. For subjects who are not eligible, the reason(s) for ineligibility must be recorded.

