The purpose of this LoA is to update the protocol as described below. New text is shown in **bold**, deleted text in ~~strikethrough~~.

1. Title page

Correct a typo in the IND number as follows: BB-IND ~~44738~~**17338**

2. Section 4.1, Inclusion Criteria

Clarify inclusion criterion #9 as follows: “White blood cell (WBC) **and** differential either within institutional normal range or accompanied by PI or designee approval”

3. Section 4.2.2, Screening

Since a witness signature on the ICF is not required, the following text is to be modified as follows: “Before screening procedures can be performed, informed consent must be obtained, and the form must be signed, dated and timed by the subject as well as signed and dated by the consentor ~~and a witness. Any member of the research/clinical team can be a witness, but a consentor and a witness should not be the same person at the same time.~~”

4. Section 4.2, Clinical Procedures and Evaluations

Add a new sub-section “*Birth Control*” to clarify that:

- **Adequate methods of reversible/temporary birth control for women generally include: abstinence; condoms, male or female, with or without a spermicide; diaphragm or cervical cap with spermicide; intrauterine devices and other prescription methods (such as contraceptive pills, hormone implants, injections, patches and others); or a male partner who has previously undergone a vasectomy.**
- **Permanent birth control for women includes:**
 - **Hysterectomy or partial hysterectomy are both forms of permanent birth control**
 - **Tubal ligation or Essure implant: FDA has prevented sales of Essure in the U.S. since Dec. 2018, but health care providers may continue to implant current devices for 1 year from date of purchase if they review the black box warning and “Patient-Doctor Discussion Checklist” with the patient.**

- **Menopausal (menses ceased for at least 1 year and no other biological or physiological cause in medical history)**

Women who have permanent birth control do not need pregnancy testing.

5. *Appendix I, Study Informed Consent Form Template*

- Under “Study Plan” clarify that the length of the study is 9 months as follows: “You will be in the study for about 36 weeks (& 9 months) and have about 9 clinic visits and 2 telephone contacts.”
- Remove the signature line for witness

6. *Appendix II, Contact Information*

- [REDACTED]

7. *Appendix III, Schedule of Evaluations*

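### Exclusion criterion 21 lists recent or treated seizures among its exceptions, so as worded it does not exclude them and it cancels its own 3-year limit on alcohol-withdrawal seizures

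*Combined protocol and SAP*

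**What the plan says.** Under Section 4.1.2 a single listed condition is enough to exclude a volunteer. Criterion 21 opens with "Seizure disorder other than: 1) febrile seizures, 2) seizures secondary to alcohol withdrawal" and continues without a break "more than 3 years ago, or 3) seizures or treatment for a seizure disorder within the last 3 years". The three items form one numbered series, joined by *or*, under one lead-in that makes each of them an exception.

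Two other criteria in the same list use *within* to mark the period that excludes: criterion 18, "Idiopathic urticaria within the last year", and part of criterion 23, "within 5 years prior to randomization, a history of suicide plan or attempt".

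Two general criteria could also apply. Inclusion criterion 6 (Section 4.1.1) requires a volunteer to be "In good general health, without clinically significant medical history, and has satisfactorily completed screening". Exclusion criterion 24 covers "Any other chronic or clinically significant medical, psychiatric or social condition that, in the judgement of the investigator is a contraindication".

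The Eligibility Review paragraph of Section 4.2.2 adds a record-keeping duty: "For subjects who are not eligible, the reason(s) for ineligibility must be recorded".

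Letter of Amendment #1 changes one eligibility criterion ("Clarify inclusion criterion #9 as follows") and leaves criterion 21 alone. Letter of Amendment #3 still amends Version 1.0 and changes only the Schedule of Evaluations. Letter #2 is not among the documents supplied.

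**The concern.** Items 1 and 2 are plainly exceptions, and the numbering makes item 3 one as well. The criterion then works against itself in three ways:

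- A volunteer with recent seizures, or under recent treatment for them, is not excluded by it.
- A volunteer whose disorder has long been inactive and untreated is excluded by it.
- The time limit in item 2 has no work to do.

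This is an operative eligibility rule in a first-in-human trial whose primary endpoint is safety. Seizures also bear on the trial's own safety rules. Section 5.2 names convulsions among its examples of medical events that may count as serious, and under Section 4.4.1 one SAE assessed as related pauses the study. A clinician who applies criterion 21 as worded and one who guesses at a different intent can reach opposite decisions on the same volunteer, and the recorded reason for ineligibility may then not match the text.

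**Working it through.** The plan gives no figure to reproduce, and no sample size, power or alpha is involved. The check is a truth table of the criterion as worded.

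**Inputs (all from Section 4.1.2, criterion 21)**

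- Item 1: the cause is febrile.
- Item 2: the cause is alcohol withdrawal and there has been no seizure in the last 3 years.
- Item 3: there has been a seizure, or treatment for a seizure disorder, in the last 3 years.

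**Formula**

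Excluded = seizure disorder AND NOT (item 1 OR item 2 OR item 3).

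**Cases**

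3 causes (febrile, withdrawal, other) × recent seizure yes/no × recent treatment yes/no = 3 × 2 × 2 = 12. *Recent* means in the last 3 years.

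| Cause | Seizure and treatment both recent | Recent seizure only | Recent treatment only | Neither |
|---|---|---|---|---|
| Febrile | exempt (1, 3) | exempt (1, 3) | exempt (1, 3) | exempt (1) |
| Alcohol withdrawal | exempt (3) | exempt (3) | exempt (2, 3) | exempt (2) |
| Other | exempt (3) | exempt (3) | exempt (3) | **excluded** |

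The numbers in brackets are the items that grant the exemption.

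**Results**

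- Excluded: 0 febrile + 0 withdrawal + 1 other = 1 of 12.
- Cases with a recent seizure or recent treatment: 3 per cause × 3 causes = 9. Excluded among them: 0 of 9.
- Withdrawal cases excluded: 0 of 4. A withdrawal seizure inside 3 years and one outside it get the same answer, so the limit in item 2 has no effect.

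**Effect of item 3**

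With item 3 ignored, NOT (item 1 OR item 2) excludes the 2 withdrawal cases with a recent seizure and all 4 other-cause cases: 2 + 4 = 6 of 12. Item 3 therefore exempts 6 − 1 = 5 further cases, and every one of them has a recent seizure or recent treatment. This comparison isolates what item 3 does; it is not a proposed rule.

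**Does the result depend on how the cases are cut?**

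The fraction does. The direction does not. With only two activity levels (recent seizure or treatment, or neither) there are 3 × 2 = 6 cases, and the same single one is excluded: 1 of 6. More generally, whenever item 3 is true for a volunteer the formula returns not excluded, whatever the cause.

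**Comparison with the neighbouring criteria**

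In criteria 18 and 23 the window marked by *within* is the excluding one. In criterion 21 it is the exempt one. That shows the list is inconsistent, but it does not establish which rule the sponsor intended.

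**The case against.** The strongest reply is that criterion 21 never acts alone. Section 4.1 requires every criterion to be satisfied, inclusion criterion 6 rules out a clinically significant history, and the sub-heading above criterion 21 itself describes the conditions listed as clinically significant. With criterion 24 added, a clinician could refuse a recent or treated case and record why.

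This reply stands in part. The general criteria may keep out an active case, so it would be wrong to say such volunteers would be enrolled. But both rest on judgement and neither names seizures. Criterion 24 is framed as covering *other* conditions, so its reach over something that criterion 21 expressly exempts is open to argument. The general criteria also do nothing in the opposite direction. For a disorder long inactive and untreated, criterion 21 read literally is decisive, because one exclusion suffices, while a clinician who takes item 3 as a ground for exclusion could admit the same person. That error costs a volunteer; it does not create a safety exposure.

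Three further points are fair:

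- **The counts.** They are counts of logical cells. They depend on the partition and treat causes as mutually exclusive. They describe the wording and do not measure harm.
- **Letter #2.** It could have corrected the criterion. The silence of Letter #3 does not show otherwise.
- **Timing.** Letter #3, dated October 24, 2019, already refers to subjects enrolled in Groups 3-6. The documents do not say that accrual had closed, but much of the benefit of a correction may be retrospective.

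**Conclusion.** The concern holds: criterion 21 is wrong as written. As worded it excludes 1 of 12 logical histories, the one with no recent activity, and 0 of the 9 with a recent seizure or treatment. It also leaves the limit in item 2 without effect. Confidence in this reading of the Version 1.0 text, as changed by Letters #1 and #3, is high; whether Letter #2 changed it could not be checked.

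The conclusion rests on reading the three numbered items as parallel exceptions, which is what the lead-in and numbering say, and on applying the criterion to a volunteer's whole history. It does not rest on any view of what the seizure rule ought to be. The documents do not say how many volunteers have such a history, so no effect on enrolment, event rates or the analysis is claimed. The point should be fixed: it is an operative eligibility rule that contradicts itself, softened but not cured by the general criteria.

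**What to change.** The sponsor should reconcile items 2 and 3 of criterion 21 with the lead-in that makes them exceptions and state the intended rule in a letter of amendment. If Letter #2 already does this, a reference to it is enough. Which seizure histories should exclude a volunteer is for the sponsor to decide; no rule is proposed here.

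The site should then check that the eligibility form carries the same rule, and that screening decisions already made under criterion 21, including recorded reasons for ineligibility, agree with it.

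The cost is one sentence, by the route Letter #1 used for inclusion criterion 9, plus the check of the form and the screening records. No subjects, visits or procedures are added.

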4.2 Clinical Procedures And Evaluations

Evaluation of this investigational vaccine will include laboratory tests, medical history, physical examination by clinicians and subject self-assessment. The schedule of study visits is shown in the Schedule of Evaluations in Appendix III.

4.2.1 Pre-screening

Subjects will be recruited through Institutional Review Board (IRB) approved advertising. To identify potential study subjects, study staff may discuss the VRC 313 clinical trial with those who express interest. Study staff may use an interview questionnaire to obtain self-reported medical history in order to determine if the subject may be eligible based on protocol inclusion and exclusion criteria. Potential subjects who appear to be eligible may continue to screen for this study. No study-specific interventions may be done during pre-screening.

4.2.2 Screening

Screening for this study will begin completed after the subject signs an informed consent form (ICF). The screening process may occur over one visit or multiple visits in order for the site to fully assess each subject's eligibility to participate in this study. Screening evaluations must all be completed within the 28-day screening window. The ICF may be signed more than 28 days before study randomization and does not need to be re-signed if outside of this window, unless required by the site's IRB or an updated form becomes available.

Assessment of Understanding: The Assessment of Understanding (AoU) is a tool to help study staff confirm the subject's understanding of the consent information. The AoU must be completed at least once before the subject signs the ICF. Incorrect answers on the AoU must be reviewed with the subject.

Study clinicians must review the ICF with each potential subject. Before screening procedures can be performed, informed consent must be obtained, and the form must be signed, dated and timed by the subject as well as signed and dated by the consentor and a witness. Any member of the research/clinical team can be a witness, but a consentor and a witness should not be the same person at the same time.

The template of the ICF is provided in Appendix I. The site must use the template to develop site-specific forms as needed, adding relevant information as required by the site institutional policies.

During Screening:

- **Medical History and Physical Examination:** Study clinicians must obtain a medical history and perform a physical examination including collection of vital signs, height and weight within 28 days before randomization.
- **Injection Site Assessment:** Clinicians should assess potential injection sites in the deltoid muscle. Clinicians should avoid administering an injection in an area that has an injury, local skin problem or significant tattoo that interferes with evaluation of the injection site after product administration.
- **Pregnancy Prevention Counseling and Pregnancy Testing:** Study clinicians must complete pregnancy prevention counseling on female subjects of childbearing potential to evaluate if subjects are able to meet the birth control eligibility criteria. Pregnancy test results must also be confirmed as negative for these subjects during screening.
- **HIV Prevention Counseling:** During screening, HIV counseling must be completed on all subjects being tested for HIV to ensure the subject is aware of how to reduce risk of and avoid HIV infection. Every attempt must be made to provide the HIV test results to the subjects.
- **Blood Sample Collection:**
 - Samples for clinical evaluation of eligibility criteria must be collected no more than 28 days before randomization. Tests may be repeated as needed based on clinical judgment to confirm eligibility or if there is a suspected change in health status.
 - Samples for research must be collected during screening per Schedule of Evaluations (Appendix III). However, research samples obtained more than 28 days before randomization do not need to be repeated. Some samples collected during screening may be used for assay validation and site proficiency testing.
- **Eligibility Review:** Based on results from the physical examination, medical history evaluation, blood tests and any additional health assessments performed during screening, the study clinicians will determine if subjects qualify to be randomized and receive the study product, and confirm this by documenting on the applicable data collection forms and in the database. For subjects who are not eligible, the reason(s) for ineligibility must be recorded.

4.2.3 Enrollment

All subjects who sign the ICF following completion of the informed consent discussion must be enrolled into the screening segment of the database.

4.2.4 Randomization

Visit 02 (Day 0) is defined as the day of study randomization and first product administration.

If a subject presents with fever or other signs of illness during the first product administration visit, do not randomize the subject and do not order or administer study product. Instead, review

the subject's medical history and conduct a targeted physical examination, as needed. If there are no exclusionary findings or significant illness and the subject becomes well, the randomization visit may be rescheduled within the 28-day allowable screening period. If Visit 02 cannot be rescheduled within the 28-day window, re-test and re-evaluate all required screening parameters in order to ensure eligibility prior to rescheduling the subject for randomization.

Before Randomization:

- **Pregnancy Prevention Counseling and Pregnancy Testing:** Pregnancy prevention counseling must be conducted, and pregnancy test results must be confirmed negative for females of childbearing potential.
- **Medical History Review and Targeted Physical Examination:** Review health status and current medications including recent vaccinations, measure vital signs, and re-assess potential injection sites.
- **Eligibility Confirmation:** Eligibility criteria must be reviewed prior to randomization in the study database.

Randomization: Subjects are electronically randomized upon entry in the database to the open dose group to receive vaccine alone or vaccine plus alum, based on a randomization plan prepared in advance by the Protocol Statistician. Randomization and product administration must both occur on the same day at Visit 02 (Day 0).

Baseline Values for Future Health Assessments: Visit 02 evaluations and medical history that were obtained prior to the first product administration will be used as the baseline for all future safety assessments. If a blood test was not performed at Visit 02 or if results were not obtained due to an error, the values that were obtained during screening evaluations may be used as the baseline for all future safety assessments.

4.2.5 Study Schedule

The Schedule of Evaluations in Appendix III provides details on the study schedule and the permitted visit windows. A clinician should discuss the target dates and timing of the study vaccination(s) and sample collections before completing a randomization to help ensure that the subject can comply with the projected schedule.

The schedule of study visits, permitted windows for completing the visits, and evaluations performed at each visit are shown in Appendix III. After randomization, deviations from the visit windows in completing study visits and study product administrations are discouraged and will be recorded as protocol deviations, but are permitted at the discretion of the IND Sponsor.

Important Information about Shifting Study Visits

Study visits are scheduled a specific number of days apart in order to obtain blood samples for safety and research data at critical time points after each product administration. Note that these days are calendar days and not working business days. Therefore, the "Day of Study" is important to consider when scheduling or rescheduling a subject visit. All study visits are scheduled based on the date of the most recent product administration. Below is further explanation on scheduling.

Visit 02 (Day 0) = first product administration visit. Study Visits 02A through 05 must be scheduled based on the date of the first product administration.

Visit 05 = second product administration visit. Study Visits 05A through 09 must be scheduled based on the date of Visit 05. For example, if Visit 05 occurs +/-7 calendar days outside of the visit window, then Visits 03A through 09 must also be moved ahead +/-7 calendar days. If the second product administration does not occur, then schedule all follow-up visits based on the date of the first product administration.

